6.0 DATA SUBMISSION

6.1 Data Collection and Submission

Data collection for this study will be done exclusively through the Medidata Rave clinical data management system. Access to the trial in Rave is granted through the iMedidata application to all persons with the appropriate roles assigned in Regulatory Support System (RSS). To access Rave via iMedidata, the site user must have an active CTEP-IAM account (check at [REDACTED]) and the appropriate Rave role (Rave CRA, Read-Only, Site Investigator) on either the LPO or participating organization roster at the enrolling site.

Upon initial site registration approval for the study in RSS, all persons with Rave roles assigned on the appropriate roster will be sent a study invitation e-mail from iMedidata. To accept the invitation, site users must log into the Select Login [REDACTED] using their CTEP-IAM user name and password, and click on the “accept” link in the upper right-corner of the iMedidata page. Please note, site users will not be able to access the study in Rave until all required Medidata and study specific trainings are completed. Trainings will be in the form of electronic learnings (eLearnings), and can be accessed by clicking on the link in the upper right pane of the iMedidata screen.

Users who have not previously activated their iMedidata/Rave account at the time of initial site registration approval for the study in RSS will also receive a separate invitation from iMedidata to activate their account. Account activation instructions are located on the CTSU website, Rave tab under the Rave resource materials (Medidata Account Activation and Study Invitation Acceptance). Additional information on iMedidata/Rave is available on the CTSU members’

website under the Rave tab at [REDACTED] or by contacting the CTSU Help Desk at [REDACTED] or by e-mail at [REDACTED].

A Schedule of Forms is available on the Alliance study webpage, within the Case Report Forms section.

6.2 Patient questionnaire booklets

All patient questionnaire booklets for A221502 are to be ordered prior to the registration of any patients. Baseline booklets will be administered in clinic at the time that the patient is randomized. Samples of all questionnaire/booklets are available in Appendices I and II, for reference and IRB submission only. **They are not to be used for patient completion.**

Post-surgery booklets (month 3 and month 6) should be mailed by institutional staff to patients 1 week before the 3 and 6 month time points. Patients will be instructed to mail the booklets back to their registering site for entry into the iMedidata RAVE.

6.3 Hospital records

Submission of hospital records listed in Appendix IV will be required. Dates of admission, surgery and discharge must be included with these records. Hospital records must be de-identified by institutional staff before mailing to [name] staff. Site personnel MUST remove all protected health information (PHI) from the medical records (including but not limited to):

[figure not shown]
- Patient name
- Patient initials
- Date of birth
- Phone numbers
- Social security number
- Medical record number or account number
- Any unique identifying number, characteristic or code

The Alliance patient ID number **must** be included on each page. De-identified hospital records should be mailed to:

[name] staff will provide participating sites with pre-addressed postage paid envelopes.

7.0 STUDY INTERVENTION

7.1 Intervention group procedures

Patients who are randomized to the intervention group will start the Pulmonary Rehabilitation (PR) within 7 days after randomization. The PR will consist of 10 sessions with the interventionist lasting less than 2 hours each. Patients will receive a Participant Manual demonstrating and explaining the rehabilitation process. Patients will also receive a log for recording their efforts and notes for every day until the day of surgery. We will consider 6 sessions as the minimum to be deemed a complete intervention (for analysis purposes). The patients should not be asked to come only 6 times to the clinic. In case of missing sessions, the patient should be encouraged to do the sessions at home, however, they will not be counted as intervention sessions.

Using the video recording during Pulmonary Rehabilitation sessions:

A video recording of the intervention from start to finish will be provided to all patients in the intervention arm. The recording will be an mp3 file that can be played from any device (e.g., phone, computer). Alternatively a CD that has the breathing practice may be used. Patients may keep the DVD/CD. The DVD should be used during the intervention with the participant. The patient and interventionist should both follow the video. This ensures that the same intervention is being delivered.

The video recording should be played in all 10 sessions at the registering site. Following the video recording will add uniformity to the intervention across sites. The interventionist can stop the video recording any time during the session to give instructions or answer questions.

Modifications may be made if needed. For example, if the patient has shoulder injury and cannot lift arms over head, then the exercise may be modified to accommodate the patient.

PR sessions will include the following components:

The patient will document in a log that they completed each component of the rehabilitation. The patients will be asked to return the log to the registering site at the end of their last PR session.

7.1.1 Breathing Awareness (in clinic): Before and after each session, the patient will do a 3-minute mindful breathing awareness exercise guided by an audio recording provided either as a CD or mp3 file. We provided also an ultra-short 10 Breath Practice that can be used during the day and at times when there are worsening symptoms (i.e. pain after surgery).

7.1.2 Upper and lower extremity exercise (in clinic): Strength and stretching exercises (goal of at least 20 minutes per session), treadmill or hallway walking (preferred) with a goal of total 24 minutes per session (not less than 18 minutes). The sites and patients will be provided a DVD that demonstrates the rehabilitation session from start to finish.

It is acknowledged that it could be “boring to have a recording” or follow a movie every time but that will provide consistency of the intervention across sites. Patients are expected to engage in walking once daily and complete the IMT routine and upper extremity exercises.

7.1.3 Instructions for Inspiratory Muscle Training (IMT) performed using the Pflex valve (Philips Healthcare Andover, MA) (in clinic): Patients will be instructed to inhale deeply and forcefully for 2 seconds and exhale normally. Repeat for one minute and rest for 30 seconds for a total of 10 complete cycles (training plus resting time). Patients are asked to adjust their trainer (there is a selector with different levels of effort) to a level of perceived exertion of “Somewhat Hard to Hard” (11-13 on the 6-20 BORG scale) when they breathe through the device. When patients note perceived exertion less than “Somewhat Hard”, the next IMT setting is increased to achieve the desired effort. The rationale to include routine use of inspiratory muscle training, not recommended as a routine in the current PR guidelines, is based primarily on a recent large randomized study which showed decreased postoperative complications.²⁰⁻²²

The table below lists the exercises that are part of the PR sessions.

Exercise	Time	Description
Breathing Awareness	3 Minutes	3 minute breathing practice at start of session
Upper Extremity	20 Minutes	Neck, Shoulder, Arm Movements
Lower Extremity	18-24 Minutes	Goal is 4 six Minute Walks, but not less than 3
P-Flex	15 Minutes	10 one minute repetitions with 30 second breaks in-between
Breathing Awareness	10 Breaths	10 Breath practice at end of session

7.1.4 Practice at home:

One-on-one revision of the IMT technique will be completed every session in the lab, and patients will be asked to do 10 repetitions of IMT twice a day when not in the lab, which includes the weekend. Twice a day training is the minimum required.

Upper and lower extremity training: Once a day training of one set of ten repetitions of upper extremity exercises, and two 6 minute walks in a safe place in the home is the minimum required.

This is a critical step in the process. Patients will be encouraged to practice every day and record their practice into a log that will be reviewed by the interventionist every session.

7.1.5 Goal setting

The patients are encouraged to set goals, a post-operative goal and post hospital discharge goal. The patients do not record the goals.

Post-operative goals will be to do at least one six minute walk, one upper arm series every day while still in the hospital. Patients will also be asked to set a goal to practice the breathing awareness, ten breaths, at least two times a day, particularly when in pain or stressed.

Post hospital discharge goals the same as post-operative goals.

7.2 Control Group Procedures

Patients randomized to the control arm will receive a pedometer to monitor their daily steps and a pamphlet with exercises plus the standard course of care for patients undergoing lung resection

surgery. The patients will not be asked to return the pedometer. The local institutional coordinator (not the rehabilitation interventionist) will go over the use of the pedometer and the exercise materials with the patient. The patients will be asked to keep a log of their pre-operative steps and mail the log to the registering site. The pedometers will be provided to the site prior to enrollment.

8.0 ADVERSE EVENTS

We do not anticipate any adverse events related to participation in this study. PR has no reported risks based on 3000 patients with severe COPD in the National Emphysema treatment trial that underwent exercise training in more intensity compared to the one planned in this study.²³

9.0 MEASURES

9.1 Chronic Respiratory Questionnaire (CRQ):

A 20-question inventory assessing the areas of dyspnea, fatigue, emotion, and feelings of mastery. The fatigue, emotion, and mastery subscales ask the patient to rate how often in the last two weeks they have been afflicted with a particular feeling or experience on a scale of 1 to 7, with higher ratings indicating less symptom impairment. The dyspnea subscale gives an additional option of indicating that a particular activity has not been done.²⁴⁻²⁷ The CRQ takes approximately 10 minutes to complete.

9.2 MRC: Medical Research Council Dyspnea Score (MRC):

A 5 statement questionnaire where the patient selects the answer that most closely describes the level of physical activity that precipitates their shortness of breath. The highest selected statement (more severe) is the score. The MRC Dyspnea Scale takes less than 5 minutes to complete.

9.3 Linear Analog Self-Assessment (LASA):

A 5 question inventory measuring well-being on a scale of 1 (as bad as it can be) to 10 (as good as it can be). The LASA takes less than 5 minutes to complete.

10.0 END OF INTERVENTION

10.1 Duration of Treatment

Patients in the intervention group will be scheduled for 10 sessions of mindful rehabilitation. Six sessions is the minimum requirement. Patients will be followed until 6 months following surgery.

10.2 Managing ineligible patients and registered patients who never receive protocol intervention

Definition of ineligible patient: A study participant who is registered to the trial but does not meet all of the eligibility criteria is deemed to be ineligible.

Follow-up for ineligible patients who continue with protocol treatment

Patients who are deemed ineligible after registering may continue protocol intervention, provided the treating physician, study chair, and executive officer agree there are no safety concerns if the patient continues protocol intervention. All scans, tests, and data submission are to continue as if the patient were eligible. Notification of the local IRB may be necessary per local IRB policies.

Follow-up for ineligible patients who discontinue protocol treatment

For patients who are deemed ineligible after registering to the trial, who start treatment, but then discontinue study treatment, the same data submission requirements are to be followed as for those patients who are eligible and who discontinue study treatment.

Follow-up for patients who are registered, but who never start study treatment

If surgery is cancelled after registration, the participant will be considered a screen failure.

For all study participants who are registered to the trial but who never receive study intervention (regardless of eligibility), baseline and off-treatment notice data submission is required. See the Data Submission Schedule accompanying the All Forms Packet.

11.0 STATISTICAL CONSIDERATIONS

11.1 Study Overview

Prospectively, 194 patients will be randomized to either ten sessions of preoperative pulmonary rehabilitation vs. standard care at a number of healthcare centers throughout the United States.

11.2 Sample Size, Accrual Time, and Study Duration

11.2.1 Sample Size

A total of 194 patients (97 in each group) will be accrued to this study. This sample size includes a 10% adjustment to account for attrition and will provide at least 80% power for testing each aim of the study. Based on estimates from the pilot study, this sample size will provide 80% power to detect a 25% difference in complication rates, a 3-day difference in chest tube days, 3 day difference in length of stay, and a half standard deviation difference in QOL endpoints.

11.2.2 Accrual Rate and Accrual Duration

This study will be open for 36 months. We expect to close the study to accrual at month 30 to allow time for statistical analysis and publication. About 7 patients a month need to be recruited to meet the 30 month proposed time line.

11.2.3 Primary Endpoint Completion Date for ClinicalTrials.gov Reporting

For purposes of ClinicalTrials.gov reporting, the Primary Endpoint Completion Date (PECD) for this study is the time the last patient registered has been followed for at least 6 months.

11.3 Statistical Design and Analysis for the Primary Endpoint

11.3.1 Primary Endpoint

End point that will address AIM 1: hospital length of stay. The coordinator at each site will be responsible for sending complete de-identified hospital records from each patient to [name] staff, where a nurse blinded to the study arm will abstract the main outcome (length of stay and postoperative complications). See Section 6.3.

The primary endpoint will be assessed at [name] office (Mayo Clinic) with the complete admission hospital records in order to extract the length of stay. The records will be mailed from the sites to [REDACTED] in a pre-stamped envelope. See Section 6.3.

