5.2 PR Manual and Training Requirements

5.2.1 General Requirements

- The individuals to be trained at each institution are those who have experience dealing with patients with chronic lung conditions.
- Institutions must name a physician, who could be a thoracic surgeon or thoracic pulmonologist to oversee the staff doing the intervention.
- The participating sites must have a space that is dedicated to the intervention. An appropriate space allows the patients to do the walking and movement exercises with the appointed trainer without disturbance.

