11.4 Supplementary Analysis Plans

11.4.1 Secondary Endpoints

End points that will address AIM 2 (baseline and at 3 and 6 months after hospital discharge):

Post-Operative Pulmonary Complications: The following events will be considered post-operative pulmonary complications: pneumonia (new infiltrate + either fever (>38.5 C) and white cell count $>11,000$ or fever and purulent secretions), severe atelectasis (requiring bronchoscopy), prolonged chest tubes (>6 days), and respiratory failure (intubation or prolonged mechanical ventilation (>24 hours)). These outcomes will be obtained by chart review by a nurse trained in the abstraction of the desired outcomes from the medical records and blinded to treatment assignment.

Chronic Respiratory Questionnaire (CRQ) (four domains: dyspnea, fatigue, emotional function and mastery). This instrument will be the primary tool to assess QoL given that it was specifically designed for COPD. Specifically, the CRQ represents one of the most well-known, widely-applied, and psychometrically-sound patient reported outcomes for use in clinical trials involving patients with COPD. The CRQ has been validated and has demonstrated a reliable quality of life measures for patients with chronic airflow limitations. A 0.5 point will be considered significant and was considered in the sample size calculation as that difference as is the well-established MCID (minimally clinically important difference) for the instrument. Analysis for the QOL outcomes will be identical to that for the primary endpoint. We include the scores from the dyspnea questionnaire under the generic umbrella term as a domain of QOL.

LASA (single-item numerical analogue quality of life Questionnaire) individual QOL domain scores. All of these questionnaires have been validated previously for lung cancer patient populations and for assessment of patient-reported outcomes in similar trials. LASA items have been validated as general measures of global QOL dimensional constructs in numerous settings and have been constructed and validated at Mayo Clinic for use in cancer patients. These single-item assessments have become the most used assessments in all NCI-sponsored cancer control studies.²⁸

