APPENDIX III: PAIN SCALE & HOSPITAL EXPERIENCE

Patient Initials: _____ Date: _____

Patient Number: _____

Directions: Please circle the answer that best reflects the level of pain that you experienced after you were discharged from the hospital.

1. Please rate your pain by using the number that best describes your pain at its worst in the last two weeks?

2. Please rate your pain by using the number that best describes your pain at its least in the last two weeks?

3. How would you rate your hospital experience?

APPENDIX IV: CHECKLIST FOR MEDICAL RECORDS**PULMONARY REHABILITATION BEFORE LUNG CANCER RESECTION**

Admission Date: _____ Discharge Date: _____ ID Number: _____

Please provide the following documents related to the Lung Surgical Resection for this study.

	YES	NO
Admission Report (Admitting history and Physical Exam)		
Operative Report (Description of procedure performed and Number of chest tubes placed)		
Discharge Summary (Dismissal information including location Subject dismissed to i.e. home, rehab facility, etc.)		
Progress Report (Daily notes including description of any complications)		
Reports of results from: Radiology (Report only, images not needed)		
Blood/Lab Draws		

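### The abstracting nurse's blinding is stated but not secured, which mainly exposes pulmonary complications; length of stay is exposed separately, if discharge is decided with knowledge of the arm.

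*Combined protocol and SAP*

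**What the plan says.** Sections 11.3.1 and 11.4.1 give the blinding. Sites send hospital records to a central office, "where a nurse blinded to the study arm will abstract the main outcome (length of stay and postoperative complications". For pulmonary complications, Section 11.4.1 repeats this: "These outcomes will be obtained by chart review by a nurse trained in the abstraction of the desired outcomes from the medical records", with the nurse again described as blinded. No other blinding of staff is described.

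The material sent is extensive. Section 11.3.1 says: "The primary endpoint will be assessed at [name] office (Mayo Clinic) with the complete admission hospital records in order to extract the length of stay". Appendix IV has a checklist that asks for the admission history, operative report, discharge summary and "Progress Report (Daily notes including description of any complications".

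Before mailing, Section 6.3 requires de-identification: "Site personnel MUST remove all protected health information (PHI) from the medical records (including but not limited to". The listed items are identifiers such as name, birth date and record number. Study arm, rehabilitation, the breathing device and the pedometer are not mentioned.

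Section 7.1.5 gives the rehabilitation arm tasks on the ward: "Post-operative goals will be to do at least one six minute walk, one upper arm series every day while still in the hospital", plus breathing practice. Under note 1 to the calendar in Section 5.5, sites mail the patient logs of both arms to the Section 6.3 address.

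On oversight, Section 5.2.1 says: "Institutions must name a physician, who could be a thoracic surgeon or thoracic pulmonologist to oversee the staff doing the intervention".

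**The concern.** Rehabilitation cannot be hidden from the patient or from those who deliver it, so this trial depends on masking whoever measures the outcome. Two separate weaknesses remain.

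**The nurse may learn the arm.** She reads free-text notes that were cleared of identity but not of allocation, and her office receives logs that differ by arm. Some complications need judgement. Pneumonia, for example, requires her to match a new infiltrate with fever and either a white cell count or purulent secretions across several notes. If she knows the arm, borderline cases can be read differently.

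**The treating team may know the arm.** Length of stay and the chest-tube component (more than 6 days) follow from bedside decisions taken before any abstraction. Blinding the nurse cannot correct a date set by someone who knew the allocation. The Background describes the programme as likely very effective, so any lean would probably be in the hypothesised direction.

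What is at stake is a favourable result that reflects recording or discharge habits rather than recovery.

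**Working it through.** **Step 1. Which route reaches which outcome.**

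| Outcome | Nurse learns the arm | Treating team knows the arm |
|---|---|---|
| Length of stay (dates required by 6.3) | Hardly affected | Exposed |
| Pneumonia | Exposed (chart judgement) | Possibly, through what is investigated and charted |
| Atelectasis needing bronchoscopy; chest tube >6 days; intubation or ventilation >24 hours | Less exposed (procedures and durations) | Exposed (team decisions) |

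**Step 2. Can the records and post reveal the arm?** The removal list in 6.3 is open-ended, but it extends protected health information, and study arm is not an identifier. The ward exercises in 7.1.5 belong to the rehabilitation arm only and could appear in the daily notes. The logs reveal the arm by their content: rehabilitation components under 7.1, step counts under 7.2. They go to the address used for the records, and no separation from the nurse is described.

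**Step 3. The plan's own figure.** Section 11.2.1 gives 97 per arm including 10% for attrition. 97 × 0.9 = 87.3, so about 87 per arm are evaluable; conversely 87/0.9 = 96.7, rounded up to 97. No SD for length of stay is given, so the 3-day claim cannot be reproduced. Solving for the SD that gives exactly 80% power:

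SD = 3 / [(1.960 + 0.842) × √(2/87)] = 3 / (2.802 × 0.1516) = 7.06 days.

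The plan claims at least 80% power for each aim, so 7.06 is nearer an upper limit than an estimate. A range of 3 to 7.06 is used below as an assumption.

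**Step 4. Illustration for length of stay.** Assume no true effect, 87 per arm, a two-sided t-test at 0.05, and rehabilitation patients discharged *b* days earlier only because the arm is known. The noncentrality is b / (SD × √(2/87)), with 172 degrees of freedom.

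| SD (assumed) | Standard error | b = 0.5: noncentrality, type I error | b = 1: noncentrality, type I error |
|---|---|---|---|
| 7.06 | 1.07 | 0.47, 7.5% | 0.93, 15% |
| 5 | 0.76 | 0.66, 10% | 1.32, 26% |
| 3 | 0.45 | 1.10, 19% | 2.20, 59% |

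Section 11.3.2 moves to a Wilcoxon test if the data are skewed, and these figures would then change.

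**Step 5. Illustration for complications.** Assume equal true rates p, with 20% of events unrecorded in the rehabilitation arm only, so that its observed rate is 0.8p. The chance of a significant result favouring rehabilitation, from a normal approximation with 87 per arm, is

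Φ{[0.2p − 1.96√(2p̄(1−p̄)/87)] / √[(p(1−p) + 0.8p(1−0.8p))/87]}, where p̄ = 0.9p.

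For p = 0.5: (0.100 − 0.148)/0.075 = −0.64, giving 26%. For p = 0.3 the result is 14%. The nominal figure in that direction is 2.5%. Fisher's exact test, which the plan uses, is more conservative: summing over both binomial distributions gives about 11% at p = 0.3 and 23% at p = 0.5. The 20% is assumed.

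**The case against.** Open delivery is inherent in supervised exercise, and the plan does more than many: central abstraction by a nurse stated twice to be blinded, a control arm instructed by someone other than the interventionist, and surgery scheduled before registration. Most complication components have explicit thresholds or procedures, which limits judgement. The supervised sessions and the step log are pre-operative while the records are inpatient, so notes may seldom mention them, and a pedometer entry on the ward is unlikely. The half-day and one-day shifts have no source in the documents.

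Much of this stands. It limits the size of the risk but does not remove it. The ward exercises and the routing of logs are firmer grounds than a chance mention of a pedometer, and neither is dealt with in the plan.

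Three stronger readings are tempting but not supported:

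- A reader might infer that the surgeon who sets the discharge date oversees the intervention. Section 5.2.1 only permits a thoracic surgeon in that role, with a pulmonologist as an alternative, and no section says who decides discharge or chest-tube removal.
- A reader might infer that incomplete redaction biases both main outcomes. Length of stay is computed from dates, so an unmasked nurse could hardly change it.
- A reader might take the error rates as estimates of bias in this trial. They show sensitivity to assumed values only.

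**Conclusion.** The point holds in a limited form. The plan claims a blinded abstractor but does not protect that blinding in the records or in the post, and the outcome mainly at risk is the chart-judged pulmonary complications, a secondary endpoint. Separately, the plan does not stop the operating surgeon from overseeing the intervention, so length of stay and the chest-tube component may rest on decisions made with knowledge of the arm. That second part depends on the inference that the surgical team decides discharge, and an open design cannot remove the risk fully.

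The documents show a risk of bias, not its occurrence, and its size cannot be derived from them. Across assumed SDs of 3 to 7.06 days, a half-day shift would give a type I error of 7.5% to 19%, and a one-day shift 15% to 59%. This is an inexpensive improvement worth making, not a flaw that invalidates the design.

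**What to change.** - **Section 6.3.** Add to the items that sites remove: *any mention of study arm, rehabilitation sessions, training device, study exercises or pedometer*.
- **Section 5.5, note 1.** Send patient logs to a recipient other than the abstracting nurse.
- **Sections 11.3.1 and 11.4.1.** Have the nurse record for each patient whether she could tell the arm, so that the success of blinding can be reported.
- **Section 5.2.1 (weaker, optional).** Ask that, where another eligible physician exists, the one overseeing the intervention is not the patient's operating surgeon.

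The first three protect the complication endpoint and do nothing for discharge timing. Only the fourth bears on length of stay, and only in part. The cost is a few more minutes of redaction per record, a second mailing destination and one extra item on the abstraction form. Separating the physicians may not be possible at small sites, and the ward cannot be fully masked, so the report should state the remaining risk for length of stay.
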